3.4 Randomisation

Not applicable for this study.

3.5 Blinding

Not applicable for this study.

3.6 Sample Size

Approximately 60 subjects are planned to be enrolled in the study. A total of 120 treated eyes is considered sufficient to characterise the immunological profile of bilateral timrepigene emparovovec administration, which is the key concern of gene therapy re-administration.

4 Statistical Methodology

4.1 Analysis Sets

The ‘All Treated Subjects’ analysis set will consist of all subjects who complete the ‘Day of Surgery’ visit of Period 1 (or, of Period 2, for subjects who received timrepigene emparvovec treatment in SE1 in an antecedent study). All Treated Subjects analysis set will be the primary population for demographics, baseline characteristics, safety and efficacy analyses.

The ‘Immunogenicity’ analysis set will include all subjects from the ‘All Treated Subjects’ analysis set with baseline sample and at least one post-surgery sample evaluable for immunogenicity. The Immunogenicity analysis set will be used for the immunogenicity analyses.

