9.4 Vitrectomy Procedure and Injection of AAV2-REP1

Injection of AAV2-REP1 is to be performed by an appropriately qualified and experienced retinal surgeon. All surgeons must have completed surgical training and obtained certification by NightstaRx to perform the study procedure, before treating a study participant. Training conducted as part of a previous AAV2-REP1 clinical trial or alternative AAV NightstaRx-sponsored gene therapy trial, can be used as the basis for approval.

Due to the complexity and unpredictability of detaching the retina in CHM, in which the retina and choroid can be extremely thin and fused in places, a modification to the technique of sub-retinal gene therapy has been developed. This involves performing the vector delivery in 2 steps after vitrectomy. An advantage of a 2-step procedure is that any unexpected complications of retinal detachment can be managed conservatively, minimising concerns about the vector escaping into the vitreous. Further, the injection could be deferred until a later date if, for instance, a macular hole was created which required treatment with gas. Also, since the volume of fluid required to detach the fovea is variable, by removing the vector from the first step, a precise consistent dose in terms of genome particles can still be applied into the sub-retinal space.

Initially, subjects will undergo a standard vitrectomy and detachment of the posterior hyaloid in the respective study eye ([Figure 2](#)). All surgeries will be conducted using the standard BIOM vitrectomy system. A 23-gauge sutured approach is usually favored to avoid any potential risks of wound leakage. The retina will be detached with 0.1-0.5 mL of balanced salt solution (BSS) injected through a 41-gauge sub-retinal cannula connected to a vitreous injection set.

[figure not shown]
In the second step of the procedure, the BSS cannula is removed from the eye and AAV2-REP1 is prepared for injection. A dose of up to 1.0×10^{11} gp of AAV2-REP1 is injected into the sub-retinal space through the same entry site. To improve visualization of the vector and facilitate dosing, surgeons are given the option of adding a minute quantity of trypan blue ophthalmic solution (~6 μ L) to the vector solution. See the GEMINI Surgical Manual for further details.

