13.3 Analysis Sets

The ‘All Treated Subjects’ Analysis Set will consist of all subjects who attend the ‘Day of Surgery’ visit of Period 1 (or, of Period 2, for subjects who received AAV2-REP1 treatment in SE1 in an antecedent study). The All Treated Subjects Analysis Set will be the primary population for demographics, baseline characteristics, and safety and efficacy analyses.

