4.3 Definitions

Study Eye 1 (SE1) is defined as the first treated eye (within GEMINI or in an antecedent clinical trial). **Study Eye 2 (SE2)** is defined as the second treated eye (irrespective of whether the first eye was treated in GEMINI or in an antecedent clinical trial). Subjects whose first eye is treated in an antecedent study will contribute to Period 2 only (except for the immunogenicity analyses), where Study Eye 1 is the eye treated in the antecedent study and Study Eye 2 is the eye treated in GEMINI.

Period 1 starts on the day of the surgery of the first treated eye and ends on the day prior to the day of the surgery of the second treated eye. **Period 2** starts on the day of the surgery of the second treated eye.

Baseline Value of Period 1/2 is defined as the last non-missing value prior to treatment of the respective period. Baseline of each period for each eye will be used to calculate the change from baseline for the data in the same period and same eye. For example, period 1 SE1 baseline will be used to calculate the change from baseline for all the data of SE1 in period 1, whereas period 2 SE1 baseline will be used to calculate the change from baseline for all the data of SE1 in period 2.

For immunogenicity, baseline will be defined separately in [Section 4.17.11](#).

Analysis day for all the post-baseline visits will be calculated as the date of the post-baseline visits minus the corresponding injection date, depending on which baseline that was used.

For the 6 subjects whose first eye was treated in the antecedent study (Subjects [REDACTED], [REDACTED], [REDACTED]), only period 2 data are collected in GEMINI. Therefore, only period 2 data will be presented for these 6 patients.

Change from Baseline is defined as the difference of the value of an assessment at the considered visit from the baseline value of the corresponding period.

Duration is measured in days and is calculated as end date – onset date + 1.

Injection dates of SE1 and SE2 will be coded **Day 0** for the Period 1 and Period 2 respectively.

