4.17 Safety Analysis

Safety analysis will be performed on the All Treated Subjects analysis set using observed cases only.

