4.20 Changes in Planned Analyses from the Protocol

There are some changes to the planned analyses described in the protocol.

1. The protocol refers to the assessment of Fixation Location. Because of a change in the way microperimetry data are collected, fixation location is not available in the database. Therefore, Fixation Location was removed from the SAP.
2. The protocol mentions that specific analyses of the sensitivity points (microperimetry) will be performed. These analyses are not included in the SAP as they are considered as exploratory across the BIIB111 program and will be performed as post-hoc analyses, if needed to be consistent with other studies in the same program.
3. For consistency of other studies in the program, time to resolution of AEs will not be summarized.
3. The protocol specifies that LOCF will be used as imputation method for efficacy analyses. The main analyses of categorical and continuous efficacy endpoints will use the observed case method, as the main purpose of the study is the evaluation of BCVA from a safety perspective. Additional supportive analyses of BCVA-related endpoints, including LOCF imputation, will be applied and are described in detail in [Section 4.16.1](#).

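### SAP 4.1 narrows the only safety population without declaring it, and SAP 4.3 anchors Day 0 and baseline to the injection, so an aborted or deferred surgery can be left out or re-baselined after the harm

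*SAP*

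**What the plan says.** **Analysis set.** In Protocol 13.3 the "Analysis Set will consist of all subjects who attend the" Day of Surgery visit of Period 1 (Period 2 if the first eye was treated in an antecedent study). In SAP 4.1 the "analysis set will consist of all subjects who complete the" same visit. The SAP does not say what completing it means. SAP 4.17 states: "Safety analysis will be performed on the All Treated Subjects analysis set using observed cases only". The Immunogenicity set is a subset of it.

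**Declared changes.** SAP 4.20 opens with "There are some changes to the planned analyses described in the protocol" and lists four: fixation location, sensitivity points, time to resolution of adverse events, and LOCF. The move from attending to completing is not among them.

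**Time anchors.** SAP 4.3 codes the injection dates as Day 0, and analysis day "will be calculated as the date of the post-baseline visits minus the corresponding injection date". Baseline "is defined as the last non-missing value prior to treatment of the respective period". Table 2 in SAP 4.16.1, used for the supportive Study Eye 1 analysis, takes the last assessment up to and including Day 0. Each period, by contrast, starts on the day of surgery of a treated eye.

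**Eye labels.** In SAP 4.3, SE2 "is defined as the second treated eye"; in SAP 3.1 the investigator numbers both eyes during Screening.

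**Surgery without same-day injection.** Protocol 9.4 describes a two-step procedure in which "the injection could be deferred until a later date if, for instance, a macular hole was created which required treatment with gas".

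**The concern.** The intervention is a vitrectomy with retinal detachment followed by a vector injection, and the protocol accepts that the first step can happen without the second on the same day. The subjects to whom that happens have had a surgical complication, which is what a safety study needs to count.

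Two parts of the SAP handle them poorly. The set definition makes inclusion depend on an undefined notion of completion, narrower than the protocol's. The injection-based Day 0 and baseline can move the reference value to a point after the complication. Either route makes the result look safer, and no second safety population exists to show the difference.

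**Working it through.** The plan has no formal sample-size or event-rate figure to reproduce here. The check is a reading of the definitions followed by illustrative arithmetic.

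**1. Who can leave the set.**
- First-eye surgery aborted and never followed by a completed surgery visit: in the set under Protocol 13.3; undetermined under SAP 4.1.
- Period 2 surgery aborted in one of the 6 antecedent-study subjects: likewise undetermined.
- Injection deferred and later given: in the set under both.
- First eye treated in this study, second-eye surgery aborted: in the set under both, through Period 1. What becomes unclear is the SE2 label and the start of Period 2.

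**2. What becomes baseline when injection is deferred.** SAP 4.15 describes the treatment as one injection, so baseline before treatment reads as before injection; Table 2 gives the same result through Day 0. BCVA is among the minimum assessments at unscheduled visits (Protocol 10.10), so a value between the complicated surgery and the later injection is plausible. Assumed example: 75 letters pre-operatively, 55 after the complication, 58 at Month 12.
- Change from the pre-operative value: 58 − 75 = −17, a loss of at least 15 letters in the SAP 4.17.1 table.
- Change from the pre-injection value: 58 − 55 = +3, no loss.

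If the injection is never given, Day 0 and analysis day are undefined for that eye.

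**3. The second eye.** Protocol 10.2 calls for SE2 treatment to wait 3 months after intraocular surgery in that eye, about 365.25/4 = 91 days. The SE2 baseline must fall within 10 weeks = 70 days of surgery (Protocol 7.1); the SAP schedule says 12 weeks = 84 days. If the first, complicated vitrectomy counts as intraocular surgery (an assumption), 91 exceeds both 70 and 84, so a baseline taken after the complication would be required.

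**4. Effect of omitting subjects.** Assume 3 events in 60 subjects, with k of them left out. The rate is (3 − k)/(60 − k). Clopper-Pearson limits (the SAP 4.2 method) are the 0.025 quantile of Beta(x, n − x + 1) and the 0.975 quantile of Beta(x + 1, n − x); the lower limit is 0 when x = 0.

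| Omitted | Rate | 95% CI |
|---|---|---|
| 0 | 3/60 = 5.0% | 1.0 to 13.9 |
| 1 | 2/59 = 3.4% | 0.4 to 11.7 |
| 2 | 1/58 = 1.7% | 0.0 to 9.2 |
| 3 | 0/57 = 0% | 0 to 6.3 |

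**5. How likely such a case is.** No rate is given. For an assumed rate q of surgery without same-day injection, P(at least one) = 1 − (1 − q)^n, treating surgeries as independent.

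| q | n = 60 first-eye surgeries | n = 120 surgeries |
|---|---|---|
| 1% | 45% | 70% |
| 2% | 70% | 91% |
| 5% | 95% | 99.8% |

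**The case against.** Much of the SAP is already tied to surgery. Treatment-emergent status runs from the day of the first surgery, adverse events go to Period 2 by the SE2 surgery date, periods start on a surgery day, and the immunogenicity baseline precedes surgery. A complication at a first attempted vitrectomy is therefore already treatment-emergent for anyone in the set, and an all-AE listing is planned. This stands: a reader might infer that the SAP's definitions as a whole turn on vector delivery, and they do not.

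Completing a visit does not literally require an injection, since Visit 1 also includes an examination, adverse event monitoring and a medication review. This stands too. Exclusion is possible, not prescribed, and the text does not support a reading that subjects with complications are systematically dropped.

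The baseline wording also appears in Protocol 13.4, and SAP 3.2 describes vitrectomy and detachment under study treatment, so the injection reading is not the only one. But Day 0 is explicitly the injection date, and SAP 4.15 favours that reading. With surgery and injection on the same day there is no effect on BCVA, because none is scheduled at Visit 1.

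A reader might also infer that subjects whose second eye is withheld have no place in the tables. SAP 3.1 numbers both eyes at Screening and both are examined throughout Period 1, so the need is to reconcile 3.1 with 4.3.

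Finally, Protocol 5.4's 4/79 = 5.1% gives 60 × 4/79 = 3.04 and may look like support for the 3 events assumed above. It is the frequency of serious reduced visual acuity as a drug reaction. It says nothing about how often surgery is aborted or injection deferred, so it cannot measure the bias.

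**Conclusion.** The point holds in limited form. The only safety population was narrowed from attending to completing the surgery visit, undefined and undeclared; whole-subject loss is confined to the first two cases in step 1 of the check. Separately, where injection is deferred after a complication, the SAP's Day 0 and baseline can place the reference value after the harm and remove a loss of 15 letters or more from the safety table. That depends on reading treatment as the injection and on a BCVA being taken in the interval.

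Both effects run toward apparent safety. Their size is unknown. The rates above rest on an assumed 3 events in 60 and an assumed number omitted; they show sensitivity at small counts, not an expected bias. Whether or when a deferred injection should be given is a clinical matter and is not addressed here.

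**What to change.** - **SAP 4.1:** return to the protocol's rule of attending the Day of Surgery visit, or use study surgery started, whether or not vector was delivered. The second option also differs from the protocol and must be declared in 4.20.
- **SAP 4.3 and Table 2:** define Day 0, analysis day and baseline from the first study vitrectomy in each eye, and state that the surgery day that starts a period is that first surgery. Since Protocol 13.4 says only before treatment, record this clarification in 4.20.
- **SAP 4.3 with 3.1:** define SE2 as the eye designated second at Screening, even if never treated.
- **Listing:** list every eye that had study surgery with deferred or no vector.
- Leave the rules for treatment-emergent status and adverse event period assignment as they are.

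The cost is SAP wording and derivation code. No new data are needed.

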4.2 Conventions

Summary statistics will be presented for continuous variables, by way of number of subjects, mean, standard deviation (SD), median, first and third quartiles (Q1 and Q3, respectively), 5th and 95th percentiles (P05 and P95, respectively), minimum and maximum. For categorical variables including binary variables, counts and percentages will be presented. Percentages will be calculated using the total number of eyes in the respective column or the total number of eyes with an assessment, the total number of treated subjects, depending on the nature of the analysis.

In addition, 95% 2-sided confidence intervals (CIs) will be presented, where specified. The 95% CI of the mean value of an assessment will be calculated using the t-test formula. The 95% CI of the mean of change from baseline of an assessment will be calculated using the t-test formula. In case of percentages, the CI will be computed using the Clopper-Pearson method. (See [Section 4.21](#) for the corresponding SAS code).

No formal statistical comparison will be performed.

Summary statistics will be presented by period and overall for all endpoints. For selected endpoints (see details below), summary statistics will also be presented by Surgery Window (Short [<6 months], Medium [6-12 months] and Long [>12 months]) and overall. Where appropriate, summary statistics will be displayed by eye (SE1 and SE2), and by period.

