4.16.4 Macular Integrity Assessment Microperimetry

Mean Sensitivity, Bivariate Contour Ellipse Area 63%, Bivariate Contour Ellipse Area 95% and Fixation Losses will also be summarised by visit, by eye, by period as well as overall. The corresponding 95% CIs will be calculated (See [Section 4.2](#)).

The number and percentage of subjects within each category of Fixation Stability will be summarised by visit, by eye, by period and by surgery window as well as all surgery windows combined. Shift from baseline will also be evaluated.

The categories for the shift from baseline for ‘Fixation Stability’ assessment are defined as follows:

- Stable at Baseline to Stable
- Stable at Baseline to Relatively Unstable/Unstable
- Relatively Unstable/Unstable at Baseline to Stable
- Relatively Unstable/Unstable at Baseline to Relatively Unstable/Unstable

Where microperimetry data are collected using the automated text files, the following algorithm will be used to define the value of Fixation Stability.

- If $P1 \geq 75\%$, then fixation stability is considered as stable.
- If $P1 < 75\%$ and $P2 \geq 75\%$, then fixation stability is considered as relatively unstable.
- If $P1 < 75\%$ and $P2 < 75\%$, then fixation stability is considered as unstable

Image quality will be listed only. This includes image completeness, focus/clarity and field definition.

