4.21 Algorithms/SAS Codes

- **Descriptive statistics for continuous variables:**

```
PROC UNIVARIATE DATA=dset NOPRINT;
  VAR var1 var2 var3 ...varn;
  BY byvar; (optional)
  OUTPUT OUT=outname
  N=n MEAN=mean MIN=min MAX=max MEDIAN=median STD=std
  P5=p5 P95=p95 Q1=q1 Q3=q3;
RUN;
```

- **95% CIs for continuous variables – ttest formula:**

```
DATA outdata;
  SET outname;
  LCL=mean-(TINV(0.975,n-1)*(std/SQRT(n)));
  UCL=mean+(TINV(0.975,n-1)*(std/SQRT(n)));
RUN;
```

- **Frequency counts:**

```
PROC FREQ DATA=dset NOPRINT;
  BY byvar; (optional)
  TABLES var1*var2;
  OUTPUT OUT=outname;
RUN;
```

- **Clopper-Pearson 95% CIs within group for binomial proportions:**

```
DATA outdata;
  SET outname;
  p=round ((x/n),0.0001);
  if p=0 then LCL=0;
  if p=1 then UCL=1;
  if p ne 0 then LCL=round((1-betainv(.975,(n-x+1),x)),.0001);
  if p ne 1 then UCL=round((1-betainv(.025,(n-x),x+1)),.0001);
RUN;
```

5 Tables and Listings

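### The SAP's confidence intervals count records, not subjects, so the undefined 'overall' rows for BCVA and microperimetry would be mis-calibrated wherever a subject appears more than once

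*SAP*

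**What the plan says.** SAP 4.2 sets two interval methods and no others. For means (and, in the same words, for changes from baseline): "The 95% CI of the mean value of an assessment will be calculated using the t-test formula". For proportions: "In case of percentages, the CI will be computed using the Clopper-Pearson method". Both are two-sided 95% intervals, given where specified.

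SAP 4.21 gives the code. The mean uses "LCL=mean-(TINV(0.975,n-1)*(std/SQRT(n" and the proportion uses "if p ne 0 then LCL=round((1-betainv(.975,(n-x+1),x)),.0001". In both, n is the count of records in the BY group. There is no subject, cluster or repeated-measures term. The denominator may be eyes: "Percentages will be calculated using the total number of eyes in the respective column".

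SAP 4.2 also says: "Summary statistics will be presented by period and overall for all endpoints". For BCVA means, changes and letter gains (4.16.1), letter losses (4.17.1) and continuous microperimetry (4.16.4), results are to be given with 95% intervals. The microperimetry wording is that they "will also be summarised by visit, by eye, by period as well as overall", and the BCVA wording is equivalent.

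Under SAP 3.3 both eyes are examined in both periods. Under SAP 4.3 each eye takes a new baseline in Period 2, and six subjects treated earlier in another study contribute Period 2 data only. The SAP does not say what the 'overall' row pools or what n is in it.

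**The concern.** The t formula and Clopper-Pearson assume independent observations. A row for one eye, one period and one visit holds one record per subject and meets that assumption. A row that pools Period 1 with Period 2, or SE1 with SE2, holds two records from most subjects, and one that pools both can hold four. Two such records do not carry the information of two subjects.

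This is a safety study. Protocol 5.4 lists loss of visual acuity as an identified risk, and SAP 4.20 gives evaluation of BCVA from a safety perspective as the study's main purpose. No tests are planned, so the intervals are the main statement of uncertainty. The 'overall' row has the largest n and could be taken as the most precise estimate. If its interval is too short, it overstates how well a given rate of vision loss has been excluded.

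**Working it through.** **The plan's own figures.** SAP 3.6 gives about 60 subjects and 120 treated eyes: 60 × 2 = 120. There is no precision calculation to reproduce. The Clopper-Pearson code agrees with the standard beta-quantile formula; for 6 of 120 it gives 1.86% to 10.57%.

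**Assumption.** Neither document gives a within-subject correlation ρ. The range 0.3 to 0.7 is assumed, with negative values considered below.

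**Formula for a mean.** With m subjects giving two records, the rest giving one, and n records in total, the true variance of the mean relative to the SAP's is (n + 2mρ)/n. The half-width should be larger by the square root of this.

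- *Periods pooled, one eye, early visits.* 54 subjects with two records plus 6 with Period 2 only: n = 54 × 2 + 6 = 114, m = 54 (taking the six as part of the 60). √(1 + 108ρ/114) = 1.133, 1.214, 1.290 at ρ = 0.3, 0.5, 0.7. Simulated coverage of the nominal 95% interval: 92%, 89%, 87%.
- *Periods pooled, one eye, Month 12.* Subjects leave the Period 1 schedule at second surgery, and about 20 are planned for the window above 12 months. Assuming these 20 alone have both records: n = 60 + 20 = 80, m = 20. √(1 + 40ρ/80) = 1.072, 1.118, 1.162. Coverage about 93%, 92%, 91%.
- *Both eyes pooled within Period 2.* The six antecedent subjects contribute both eyes here, so m = 60 and n = 120. √(1 + ρ) = 1.140, 1.225, 1.304. Coverage about 92%, 89%, 87%.
- *Both eyes and both periods, four records each, equal correlation.* √(1 + 3ρ) = 1.378, 1.581, 1.761. Coverage about 84%, 78%, 73%. This row would also mix untreated SE2 data from Period 1 with treated-eye data.

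The pooled sample SD is also slightly too small. Allowing for this moves the first three sets by at most one percentage point (14%, 23% and 31% for the 60 pairs).

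**Sign of ρ.** For changes of one eye across two periods, ρ can be negative. If the Period 1 value Y in the row also serves as the Period 2 baseline, the two changes are Y − B and Y′ − Y. Measurement error in Y, with variance σ², then adds −σ² to their covariance. At ρ = −0.3 with 54 pairs and 6 singles, the factor is √(1 − 0.284) = 0.846 and coverage is about 98%: the interval is too wide.

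**Proportions.** Clopper-Pearson starts above 95%, so it has some slack. Coverage at ρ = 0, 0.3, 0.5, 0.7:

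| Row | True rate | 0 | 0.3 | 0.5 | 0.7 |
|---|---|---|---|---|---|
| n = 114 | 5.1% | 97% | 94% | 92% | 90% |
| n = 120 | 5% | 96.7% | 93.9% | 91.7% | 89.6% |
| n = 120 | 20% | 96.0% | 92.8% | 90.6% | 88.4% |

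The 5.1% is the rate in Protocol 5.4 for a serious adverse reaction, used only as an illustrative low rate. For 12 of 120 eyes, the SAP's interval is 5.3% to 16.8%. With effective n = 120/(1 + ρ), it is 4.7% to 18.0% at ρ = 0.3 (n = 92.3) and 4.4% to 18.8% at ρ = 0.5 (n = 80).

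**The case against.** The strongest reply is that 'overall' may not mean pooling at all. SAP 4.2 also attaches the word to surgery windows, and Table 1 in SAP 4.7 lists it as a surgery-window value. If it means all windows combined, every eye-by-period row keeps one record per subject and the problem does not arise. SAP 4.2 also calls the reported count for continuous variables a number of subjects, which sits badly with a record count.

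This stands as a real ambiguity, but the text leans the other way. The sentence in SAP 4.2 pairs 'overall' with period, and the surgery-window sentence follows as an addition. SAP 4.16.4 uses different words when it means windows combined. SAP 4.16.2 and 4.16.3 stop at visit, eye and period, so 'overall' elsewhere looks like an extra row.

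A reader might infer that every 'overall' interval is too narrow by 13% to 29%. The documents do not support that. The direction depends on a correlation they do not give, and the reset baseline could make it negative for changes across periods. The 114-record figure fits only early visits with periods pooled.

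A reader might also infer that the study's safety conclusions are undermined. They are not: AE percentages and their intervals use subjects, including overall (SAP 4.17.10); sound one-eye, one-period intervals appear alongside; and no formal comparison is planned. At a 5% rate and ρ = 0.3, Clopper-Pearson coverage is still about 94%.

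**Conclusion.** The point holds in a limited form. The SAP's interval formulas are valid only for rows with one record per subject, yet the SAP applies them without restriction and requires 'overall' rows that it does not define. If those rows pool a subject's records, the interval is mis-calibrated. It is likely too narrow for BCVA levels and for fellow eyes, where positive correlation is plausible. It may be too wide for one eye's changes across periods.

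Under the assumed correlations, the shortfall in half-width for a mean runs from about 7% (Month 12, periods pooled, ρ = 0.3) to about 30% (both eyes in Period 2, ρ = 0.7), and more if eyes and periods are both pooled. These sizes rest on the assumed ρ, on full attendance at the planned numbers and, for Month 12, on about 20 pairs. The effect is on reported precision, not on any decision rule, but it falls on the study's main vision-safety measure and is cheap to put right.

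**What to change.** In SAP 4.2:

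1. State what 'overall' pools for each endpoint (periods, eyes, both, or surgery windows only) and what n means in that row.
2. Restrict the t and Clopper-Pearson formulas, and the code in SAP 4.21, to rows with one record per subject.
3. In any row with more than one record per subject, use a subject-level or cluster-adjusted interval, or show none. For continuous measures, use a cluster-robust interval or subject means; with 60 pairs, simulated coverage of the subject-mean t interval returns to about 95%. For proportions, use Clopper-Pearson on an effective sample size, or on subjects with any affected eye.

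Both options for proportions work with zero events. A subject-level bootstrap then collapses to zero width, and robust GEE on the logit scale cannot be estimated. With zero events the upper limit is 1 − 0.025^(1/n): 3.0% at n = 120 and 4.5% at an effective n of 80. The data cannot supply ρ in that case, so a value should be fixed in advance.

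The cost is a few sentences and a short macro, with no new data. Combined-row intervals will usually be wider. Counting subjects with any affected eye changes the quantity reported, and subject means can weight subjects differently from the pooled mean when record numbers differ; the table footnotes should say so.
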